### **5.12.3. Missing Dates for Concomitant Medication**

If start date is missing or partial:

- if month is missing, use January
- if day is missing, use the first day of the month under consideration
- if year is missing, use year of the informed consent date
- if entire date is missing, use informed consent date

If stop date is missing or partial:

- if month is missing, use December
- if day is missing, use the last day of the month under consideration
- if year or the entire date is missing, set to December 31st, 2099

If the imputed start date is after the stop date, then the imputed start date will be one day prior to the stop date.

#### 5.12.4. Missing Dates for Disease Diagnosis Date

For disease diagnosis dates, the imputation rules are

- if day is missing, use 15th of the month
- if both day and month are missing, impute as January 1st
- if month is missing, impute as January
- if year is missing, set to missing

### 5.13. Changes in Conduct or Planned Analyses from the Protocol

Major changes between SAP and the planned analysis in Protocol are described below:

Item	Difference Between Protocol and SAP
NTD/TD	In SAP, the terms LTB/HTB are used in place of NTD/TD in protocol.
mITT	In the SAP, ITT is used in place of mITT in the protocol.
Secondary objectives: time to and duration of mHI-E	The secondary endpoints time to and duration of mHI-E will not be analyzed.
Efficacy Evaluable Population (EE)	Analysis on Efficacy Evaluable population will not be performed. All analyses are on ITT population
Definition of baseline hemoglobin	Protocol definition: Baseline hemoglobin will be the average of at least two measures (not influenced by transfusion within 7 days of measurement); one measure performed within one day prior to Cycle 1 Day 1 and the other performed 7-28 days prior to Cycle 1 Day 1. This definition is revised in this SAP to reflect the derivation rule implemented for this study.

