15.2.3. Secondary Analysis

Efficacy/Pharmacodynamic Effects Analysis of Secondary Endpoints:

All efficacy analyses will be performed for the EE and mITT populations.

Efficacy will be evaluated by determining the proportion of patients who have a modified HI-E erythroid response rate based upon the IWG 2006 criteria ([Appendix 5](#)), defined as 1) A mean hemoglobin increase ≥ 1.5 g/dL over an 8-week period as compared to baseline, not influenced by RBC transfusion in NTD patients or 2) A decrease of ≥ 4 units or $\geq 50\%$ of units of RBCs transfused over a period of 8 weeks, relative to the number of units of RBCs transfused in the 8 weeks immediately prior to Cycle 1 Day 1 in TD patients.

Baseline hemoglobin will be the average of two or more measures (not influenced by RBC transfusion) performed during the screening period for study A536-03 (for patients without interruption) or study A536-05 (for patients with interruption).

Baseline units of RBCs transfused will be the 8-week period prior to study A536-03 (for patients without interruption) or study A536-05 (for patients with interruption).

The erythroid response will be summarized using both a point estimate and its exact 95% confidence interval based on binomial distribution.

No direct comparison testing with concurrent or historical controls will be performed.

Analysis of other secondary efficacy/pharmacodynamic endpoints will include:

- Time to HI-E response and duration of HI-E response as per the IWG 2006 criteria and modified IWG criteria.
- Mean RBC transfusion burden
- Rate of RBC transfusion-free period lasting \geq 8 weeks in TD patients.
- Mean hemoglobin level change in NTD patients
- Other PD endpoints including:
 - Biomarkers for iron overload/metabolism
 - Relationship of biomarkers to response
 - Rates of HI-E, HI-N and HI-P

Exploratory endpoints will include:

- Biomarkers related to the TGF β superfamily.
- Patient-reported quality of life using tools including but not limited to the FACT-An questionnaire.

All binary endpoints will be summarized using both a point estimate and its exact confidence interval based on the binomial distribution. The time-to-event type secondary endpoints will be analyzed using Kaplan-Meier method to estimate the survival curve and median time to event and 95% confidence interval.

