15.5. Deviation from Original Analysis Plan

A formal Statistical Analysis Plan (SAP) for the analysis and presentation of data from this study will be prepared before the database lock. Deviations from the statistical analyses outlined in this protocol will be indicated in this plan; any further modifications will be noted in the final clinical study report.

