## 2. STUDY OBJECTIVES

Primary Objective:

- To evaluate the long-term safety and tolerability of ACE-536 in patients with low or intermediate-1 risk MDS who were previously enrolled in study A536-03.

Secondary Objectives:

- To evaluate erythroid response (modified HI-E from International Working Group [IWG] 2006 criteria), defined as proportion of patients with:
  - A mean hemoglobin (Hgb) increase  $\geq 1.5$  g/dL over an 8-week period as compared to baseline, not influenced by red blood cell (RBC) transfusion, in non-transfusion dependent (LTB) patients (refer to [Section 5.1](#) for definitions of LTB and HTB).
  - A decrease of  $\geq 4$  units or  $\geq 50\%$  of units of RBCs transfused over a period of 8 weeks, relative to the 8 weeks immediately prior to Day 1, in transfusion dependent (HTB) patients.
- To evaluate rates of erythroid, neutrophil and platelet (HI-E, HI-N and HI-P) responses (IWG 2006 criteria)
- To evaluate the rate of RBC transfusion independence lasting  $\geq 8$  weeks in HTB patients
- To evaluate time to HI-E response and duration of HI-E response (modified and non-modified IWG 2006 criteria)
- To evaluate the mean change in RBC transfusion burden in HTB patients and mean change in hemoglobin levels in LTB patients
- To evaluate the pharmacokinetic (PK) profile of ACE-536
- To evaluate other pharmacodynamic (PD) effects (e.g., iron overload/metabolism, erythropoietin [EPO], and reticulocytes)

Exploratory Objectives:

- To examine biomarkers related to the TGF- $\beta$  superfamily

- To examine self-reported quality of life using tools including but not limited to the FACT-An questionnaire

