### 5.8.2. Secondary Efficacy Endpoints

#### 5.8.2.1. Erythroid Response (modified HI-E from IWG 2006 criteria)

Erythroid response (modified HI-E from IWG 2006 criteria) is defined as the proportion of patients with:

- A mean hemoglobin (Hgb) increase  $\geq 1.5$  g/dL over an 8-week period as compared to baseline, not influenced by RBC transfusion, in LTB patients.
- A decrease of  $\geq 4$  units or  $\geq 50\%$  of units of RBCs transfused over a period of 8 weeks, relative to the 8 weeks immediately prior to Day 1, in HTB patients.

A point estimate of the proportion of patients achieving a modified erythroid response will be presented along with its associated exact 95% confidence interval based on binomial distribution.

The complete hemoglobin measurements and RBC transfusion records will be listed for each patient.

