#### 5.8.2.3. HI-E Response Rate

Erythroid (HI-E) response will be defined following IWG 2006 criteria.

- For low transfusion burden (LTB) patients, a hemoglobin increase of  $\geq 1.5$  g/dL from baseline during any rolling 8-week period in the absence of transfusion. The rolling 8-week period starts and ends at a hemoglobin measurement date with duration  $\geq 8$  weeks.

- For high transfusion burden (HTB) patients, a reduction by  $\geq 4$  RBC units transfused during any rolling 8-week interval on treatment compared to baseline.

A point estimate of the proportion of HI-E responders will be presented along with its associated exact 95% confidence interval based on binomial distribution. HI-E response will also be listed for each patient.

There are two versions of a HI-E response for LTB patients.

- All hemoglobin values increase of  $\geq 1.5$  g/dL from baseline during any rolling 8-week period in the absence of transfusion.
- Mean hemoglobin value increase of  $\geq 1.5$  g/dL from baseline during any rolling 8-week period in the absence of transfusion.

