#### **5.8.2.5. Time to and Duration of HI-E Response**

Time to and duration of HI-E response will be analyzed for HI-E responders only.

Time to HI-E response will be defined as the time from the first dose date to the first date of any rolling 8-week interval achieving HI-E response.

Duration of HI-E response will be defined as below for LTB and HTB patients, respectively:

- For LTB patients, duration of HI-E response will be calculated as the longest interval during which all hemoglobin measurements have an increase of  $\geq 1.5$  g/dL from baseline.
- For HTB patients, duration of HI-E response will be calculated for the longest such interval as the time from the start date of the first rolling 8-week interval achieving hematologic response to the end date of the last consecutive rolling 8-week interval achieving response.

When there are multiple disjoint intervals with response, the longest interval will be used. Patients with response ongoing by the analysis cutoff day will be censored at that date.

Both time to and duration of HI-E response will be analyzed as continuous variables and summarized by descriptive statistics. In addition, duration of HI-E response will also be analyzed as a time to event endpoint. The survival curves will be estimated using Kaplan-Meier method if the number of patients is more than 5.

HI-E responders may experience multiple periods of  $\geq 8$  weeks of HI-E response. For all HI-E responders, the number of episodes and cumulative duration will be summarized. As an exploratory analysis, the cumulative duration of the multiple responses will be analyzed using Kaplan-Meier method.

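### Time to and duration of modified HI-E remain a stated secondary objective, but SAP 5.13 drops both without a reason, so modified HI-E gets a rate and no durability

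*SAP*

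**What the plan says.** The protocol lists this objective in 8.2 and plans the analysis in 15.2.3: "Time to HI-E response and duration of HI-E response as per the IWG 2006 criteria and modified IWG criteria". SAP Section 2 repeats the objective: "To evaluate time to HI-E response and duration of HI-E response (modified and non-modified IWG 2006 criteria").

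SAP 5.13, the table of changes from the protocol, removes it: "The secondary endpoints time to and duration of mHI-E will not be analyzed". That row gives no reason. Protocol 15.5 provides for such changes: "Deviations from the statistical analyses outlined in this protocol will be indicated in this plan".

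What remains for each response:

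- **Modified HI-E (SAP 5.8.2.1).** "A point estimate of the proportion of patients achieving a modified erythroid response will be presented along with its associated exact 95% confidence interval", plus patient listings. In HTB patients the rule is a fall of at least 4 units or at least 50% "of units of RBCs transfused over a period of 8 weeks, relative to the 8 weeks immediately prior to Day 1, in HTB patients". In LTB patients it is a mean hemoglobin rise of at least 1.5 g/dL over 8 weeks.
- **IWG HI-E (SAP 5.8.2.3).** In HTB patients, a fall of at least 4 "RBC units transfused during any rolling 8-week interval on treatment compared to baseline", with no percentage alternative. In LTB patients there are two versions: every hemoglobin value, or the mean value, at least 1.5 g/dL above baseline.
- **Time and duration (SAP 5.8.2.5).** "Time to and duration of HI-E response will be analyzed for HI-E responders only". LTB duration is the longest stretch in which every value is at least 1.5 g/dL above baseline.
- **RBC transfusion independence (SAP 5.8.2.2).** Time to and duration of at least 8 transfusion-free weeks, for patients with at least 2 baseline units.

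**The concern.** Modified HI-E is the first secondary efficacy response listed, and the SAP still states an objective about how soon it occurs and how long it lasts. No planned analysis answers that objective. The modified and IWG rules do not select the same HTB patients, so the HI-E durations cannot simply be read across to the modified rate. The report would show a modified response rate next to durations derived under a different rule, in a study whose purpose is to describe long-term treatment. For LTB patients the duration rule itself may not match the rule that made the patient a responder.

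**Working it through.** The plan gives no figure to reproduce: there is no sample-size calculation and no hypothesis test. The check compares the rules directly and then illustrates the size.

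**1. HTB thresholds in whole units.** Let B be the baseline units in 8 weeks (HTB means B ≥ 4, SAP 5.1) and R the reduction. Modified response: R ≥ 4 or R ≥ 0.5B. IWG response: R ≥ 4.

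| B | Smallest R, modified | Smallest R, IWG | R that is modified only |
|---|---|---|---|
| 4 | 2 | 4 | 2 or 3 |
| 5 | 3 | 4 | 3 |
| 6 | 3 | 4 | 3 |
| 7 and above | 4 | 4 | none |

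The rules differ only at 4, 5 and 6 baseline units.

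**2. Does transfusion independence cover these patients?** An HTB patient with 8 transfusion-free weeks has R = B ≥ 4, which is an IWG response. So an HTB patient who never meets the IWG rule can never be a transfusion-independence responder. That patient counts in the modified rate and has no duration under 5.8.2.5 or 5.8.2.2.

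**3. LTB duration.** Take rises of 1.6, 1.3, 1.8 and 1.7 g/dL at visits 21 days apart (days 0, 21, 42, 63), with values outside this stretch below 1.5. The span is 63 days, which satisfies the 8-week (56-day) window. The mean is (1.6 + 1.3 + 1.8 + 1.7)/4 = 1.6, so the mean version is met. The all-values version fails at 1.3. The longest stretch with every value at or above 1.5 runs from day 42 to day 63, or 21 days. If 5.8.2.5 selects on the mean version, this patient gets a 21-day duration for a response defined over 8 weeks. If it selects on the all-values version, the patient gets none.

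**4. Illustrative size in HTB.** The documents give no distribution of baseline units, so two mixes over 4, 5, 6, 7 and 8 units are assumed: A = 30, 15, 20, 10, 25% and B = 20, 15, 20, 15, 30%. Units in one 8-week window are taken as X ~ Poisson(B(1 − r)), where r is the true reduction. Modified response means X ≤ 2, 2, 3, 3, 4 for B = 4 to 8. IWG response means X ≤ B − 4. The modified-only share is 1 − Σw·P(IWG)/Σw·P(modified).

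Example, mix A, r = 50%:

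- Modified: 0.30(0.677) + 0.15(0.544) + 0.20(0.647) + 0.10(0.537) + 0.25(0.629) = 0.625.
- IWG: 0.30(0.135) + 0.15(0.287) + 0.20(0.423) + 0.10(0.537) + 0.25(0.629) = 0.379.
- Share: 1 − 0.379/0.625 = 39%. Mix B gives 31%.

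SAP 5.8.2.3 searches any rolling interval on treatment, so the same model was also simulated with a daily rolling search under both rules.

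| True reduction | One window | 26 weeks, rolling | 52 weeks, rolling |
|---|---|---|---|
| 30% | 40–49% | about 19–25% | about 8–11% |
| 50% | 31–39% | about 10–14% | about 2–3% |
| 70% | 21–28% | about 3–4% | under 1% |

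The rolling figures assume a constant transfusion rate and full follow-up to the stated week. Early discontinuation or irregular transfusion would change them.

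**The case against.** The strongest reply is that the change is declared in the place the protocol provides for it. Section 2 restates the protocol's objectives, 5.13 is the operative plan, the study is descriptive with safety as its primary objective, and full hemoglobin and transfusion records are listed per patient. All of this stands. It makes the point one of completeness rather than of a hidden contradiction. It does not supply a reason for the omission or answer the objective.

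Three stronger readings are tempting, and the documents do not support them.

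- **All reported durability comes from patients meeting a stricter IWG rule.** Transfusion-independence duration is also reported and can include LTB patients with 2 or 3 baseline units who meet no IWG hemoglobin rule. The mean version of LTB HI-E is essentially the modified rule. In HTB the IWG rule is stricter only at 4 to 6 units.
- **A third or more of HTB modified responders are left out.** That follows only from a single window. Under the rolling search the share falls severalfold as follow-up lengthens.
- **The analysis was dropped because of the results.** The study is open-label and response data may be reviewed during it (protocol 15.4, SAP 5.10), but nothing in the documents shows that results prompted the change.

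A reader could also be trusted not to attach HI-E durations to the modified rate, since 5.8.2.5 says whom they describe. That is fair, but it leaves the reader with no duration for the modified response at all.

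**Conclusion.** The point holds as a gap in the plan. A stated secondary objective has no analysis and no stated reason for its removal. HTB patients with 4 to 6 baseline units who meet only the 50% rule have no duration anywhere, and the LTB duration analysis does not specify which responders it describes. The threshold comparison and the transfusion-independence argument follow from the definitions, given whole units. The shares do not: they rest on assumed baseline mixes and a Poisson model, and the true share cannot be computed from the documents.

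A reader might infer that the HI-E durations overstate how long a modified response lasts. The direction is not determined. Every window that meets the HTB IWG rule also meets the modified rule, so a given HTB patient's modified duration is at least as long as the IWG one. Adding the modified-only patients could still pull a pooled summary down. The endpoint is secondary and descriptive, so the matter is moderate, but the correction is cheap and worth making before database lock.

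**What to change.** Delete the modified HI-E row from SAP 5.13. Add to 5.8.2.5 a descriptive analysis of time to and duration of modified HI-E with the same rolling-window algorithm and the 5.8.2.1 thresholds: for HTB, a reduction of at least 4 units or at least 50%; for LTB, a rolling 8-week mean rise of at least 1.5 g/dL. Show the results by LTB and HTB beside the IWG results. State in 5.8.2.5 which LTB version of HI-E selects responders for the IWG duration.

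If the sponsor keeps the omission, the minimum is a reason in 5.13, a note against the objective in Section 2, and the named LTB version. That would make the plan consistent but leave the objective unanswered.

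The cost is SAP wording and a few more derivations and tables from hemoglobin and transfusion data already collected. The pooled modified durations may look less favourable than the IWG ones.

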## 7. APPENDICES

### 7.1. Appendix 1: List of Abbreviations

Abbreviation	Definition
AE	Adverse Event
ALT	Alanine aminotransferase
AST	Aspartate aminotransferase
BSAP	Bone specific alkaline phosphatase
BUN	Blood urea nitrogen
CRF	Case report form
CTX	C-telopeptide of type I collagen
ECG	Electrocardiogram
ECOG	Eastern Cooperative Oncology Group
EE	Efficacy Evaluable
ESA	Erythropoiesis stimulating agent
EOS	End of Study
EPO	Erythropoietin
EOT	End of Treatment
FACT-An	Functional Assessment of Cancer Therapy-Anemia Scale
HI-E	Erythroid response
HI-N	Neutrophil response
HI-P	Platelet response
HTB	High Transfusion Burden
ICT	Iron Chelation Therapy
IPSS	International Prognostic Scoring System
IPSS-R	Revised International Prognostic Scoring System
ITT	Intent-to-Treat
IWG	International Working Group
LDH	Lactate dehydrogenase
LTB	Low Transfusion Burden
LTFU	Long-Term Follow-Up
MedDRA	Medical Dictionary for Regulatory Activities
MCH	Mean corpuscular hemoglobin

Abbreviation	Definition
MCHC	Mean corpuscular hemoglobin concentration
MCV	Mean corpuscular volume
MDS	Myelodysplastic syndromes
NCI-CTCAE	National Cancer Institute-Common terminology criteria for adverse events
nRBC	Nucleated red blood cells
PD	Pharmacodynamic
PK	Pharmacokinetic
PTFU	Post-treatment Follow-up
QoL	Quality of life
RBC	Red blood cell
RDW	Red blood cell distribution width
RS	Ring Sideroblasts
SAE	Serious adverse event
SAP	Statistical analysis plan
SD	Standard deviation
SF3B1	Splicing factor 3B subunit 1
SRT	Safety Review Team
TGF- $\beta$	Transforming growth factor beta
TIBC	Total iron binding capacity
WBC	White blood cell
WHO	World Health Organization

**7.2. Appendix 2: Schedule of Events for Study 03**

	Screen	Treatment Period															Follow up period			
		Cycle 1				Cycle 2			Cycle 3			Cycle 4			Cycle 5			EOT 	Post-Treatment Follow Up	EOS 
		C1D1 	C1D8	C1D1 1	C1D1 5	C2D1 	C2D8	C2D1 5	C3D1 	C3D8	C3D15	C4D1 	C4D8	C4D15	C5D1 	C5D8	C5D15			
		Day -28	Day 1	Day 8 (± 1d)	Day 11 (± 1d)	Day 15 (± 1d)	Day 22 (± 2d)	Day 29 (± 2d)	Day 36 (± 2d)	Day 43 (± 2d)	Day 50 (± 2d)	Day 57 (± 2d)	Day 64 (± 2d)	Day 71 (± 2d)	Day 78 (± 2d)	Day 85 (± 2d)	Day 92 (± 2d)	Day 99 (± 2d)	Day 113 (± 7d)	Day 141 (± 7d)
Informed consent	X																			
Inclusion/Exclusion	X	X																		
Medical history	X																			
FACT-An Questionnaire 	X															X		X 	X	
Physical examination	X	X				X			X			X			X			X	X	
Vital signs 	X	X	X		X	X	X	X	X	X	X	X	X	X	X	X	X			
ECOG Status	X							X			X							X	X	
ECG (12 lead)	X					X												X		
Bone marrow aspirate/biopsy 	X							X										X		
Serum iron studies 	X	X				X	X		X			X			X			X	X	
Serum folate and B12	X																			
Erythropoietin levels	X	X	X		X	X						X						X	X	
Hematology 	X	X	X		X	X	X	X	X	X	X	X	X	X	X	X	X	X		
Peripheral blood smear	X	X				X								X			X			
Serum chemistry 	X	X			X	X	X		X	X		X	X		X	X		X		
Urinalysis and Urine Chemistry 		X				X						X						X	X	
Anti-drug antibody 		X										X						X	X 	
PK collection		X	X	X	X	X	X					X			X	X	X	X	X	
PD biomarkers 		X				X			X			X			X			X	X	
Bone biomarkers 		X										X						X		
Pregnancy test 	X	X				X			X			X			X			X	X	
Evaluate transfusion frequency 	X	X				X			X			X 			X			X	X	
Concomitant medications and AEs	X	X	X	X	X	X	X	X	X	X	X	X	X	X	X	X	X	X		
Administer ACE-536 		X				X 			X 			X 			X 					

 **Vital signs:** Weight, heart rate, systolic and diastolic blood pressure, respiration rate and temperature (measured in degrees Celsius). Height is measured only at Screening.

 **Study procedures** must be done prior to administration of study drug.

 **Bone marrow aspirate/biopsy** including cytogenetics at screening must be performed  $\leq$  3 months prior to C1D1 for evaluation of patient eligibility and other PD biomarkers to be determined (e.g., GDF15, GDF8, and GDF11). A bone marrow aspirate must be performed within 21 days after C3D1 (a bone marrow biopsy is not required). If hemoglobin increases  $\geq$  2 g/dL, an optional bone marrow aspirate can be performed within 7 days of the result. At the end of treatment visit, a bone marrow aspirate must be performed (a bone marrow biopsy is optional).

 **Iron Studies:** Serum iron, TIBC, transferrin, soluble transferrin receptor, ferritin.

 **Hematology:** RBC, WBC with differential, hemoglobin, hematocrit, nRBC, reticulocyte count, platelet count, MCV, MCH, MCHC, and RDW. On dosing days, hemoglobin values are to be drawn and resulted (up to 1 day) prior to dosing (see protocol Section 10.8.1, Patient Dose Modification Rules). Historical hemoglobin data will be collected for 24 weeks, where available, prior to C1D1. During the screening period, hemoglobin will be measured twice; one measure performed within one day prior to Cycle 1 Day 1 and the other performed 7-28 days prior to Cycle 1 Day 1. Neither hemoglobin measure should be influenced by transfusion within 7 days of measurement.

 **Chemistry:** Sodium, potassium, AST, ALT, lactate dehydrogenase (LDH), total bilirubin, direct bilirubin, alkaline phosphatase, blood urea nitrogen (BUN)/urea, creatinine, GGT, calcium, phosphorus, glucose, amylase, lipase, total protein, albumin, and uric acid.

 **Urinalysis by dipstick analysis (local lab):** pH, specific gravity, protein, glucose, ketones, blood, leukocyte esterase, and nitrite, with microscopic examination if indicated. **Urine Chemistry (central lab):** Microalbumin and creatinine.

 **PD Biomarkers:** Hepcidin, GDF15, GDF8, GDF11, and others to be determined.

 **Bone Biomarkers:** BSAP and CTX.

 **Pregnancy test:** (urine or serum) is required for female patients of child bearing potential at screening and prior to each dose of ACE-536.

 **Transfusion history** will be collected for 24 weeks, where available, prior to C1D1.

 **End of Treatment (EOT):** Should be performed 28 days ( $\pm$  7 days) after the last dose of ACE-536. Patients who discontinue treatment early should complete the end of treatment visit at the time of discontinuation and complete the post-treatment follow-up (PTFU) and EOS follow-up visits 28 days ( $\pm$  7 days) and 56 days ( $\pm$  7 days) after the EOT visit.

 **End of Study (EOS):** Should be performed 56 days ( $\pm$  7 days) after the Day 113/EOT visit.

 **Day 85  $\pm$  2 days** is the last possible study day that ACE-536 may be administered, regardless of the cycle.

 If a **dose delay** is required per the dose modification rules the patient will not be dosed. The patient will return weekly to assess hematology results and adverse events until the patient is eligible to administer the next dose of ACE-536.

 If the patient has a **positive ADA** result at their last assessment, the patient may be asked to return approximately every three months for additional testing, until a negative result is obtained or the result is considered stabilized.

 For the **first dose of ACE-536**, dosing should occur after a minimum of 7 days post-transfusion and a minimum of 24 hours prior to a scheduled transfusion.

 **Expansion cohort** patients only, administration of FACT-An quality of life questionnaire.

 FACT-An should be completed at the EOT visit only for patients that discontinue treatment early.

### 7.3. Appendix 3: Schedule of Events for Study 05

	Screening 	Cycle 1	Cycle 2	Cycle 3	Cycle 4	Cycle 5	Cycle 6	Cycle 7	Cycle 8	Cycle 9
		C1D1 	C2D1 	C3D1 	C4D1 	C5D1 	C6D1 	C7D1 	C8D1 	C9D1 
Informed consent	X 									
Inclusion/Exclusion	X	X 								
Medical history 	X									
QoL Questionnaires 		X				X				X
Physical examination	X	X				X				X
Vital signs 	X	X	X	X	X	X	X	X	X	X
ECOG Status	X	X		X		X		X		X
ECG (12 lead) 		X								
Bone marrow aspirate 	X	X 								X 
Serum iron studies 		X				X				X
Erythropoietin levels		X				X				X
Hematology 	X	X	X	X	X	X	X	X	X	X
Peripheral blood smear		X				X				X
Serum chemistry 	X	X		X		X		X		X
Urinalysis and Urine Chemistry 	X	X				X				X
Anti-Drug Antibody 		X				X				X
PK collection		X				X				X
PD biomarkers 		X				X				X
Pregnancy test 	X	X	X	X	X	X	X	X	X	X
Evaluate transfusion frequency 	X	X	X	X	X	X	X	X	X	X
Administer ACE-536		X	X	X	X	X	X	X	X	X
Concomitant medications and AEs	Collected Continuously									

	Cycle 10	Cycle 11	Cycle 12	Cycle 13	Cycle 14	Cycle 15	Cycles 16 - 87 	EOT 	PTFU 	LTFU 	EOS 
	C10D1 	C11D1 	C12D1 	C13D1 	C14D1 	C15D1 					
Informed consent											
Inclusion/Exclusion											
Medical history 											
QoL Questionnaire 				(X) 				X			
Physical examination					X				X		
Vital signs 	X	X	X	X	X	X		X			
ECOG Status		X		X				X			
ECG (12 lead) 								X			
Bone marrow aspirate 				(X) 				X 			
Serum iron studies 					X				X		
Erythropoietin levels					X				X		
Hematology 	X	X	X	X	X	X		X	X		
Peripheral blood smear					X			X			
Serum chemistry 		X		X				X			
Urinalysis and Urine Chemistry 					X			X			
Anti-Drug Antibody 					X			X 			
PK Collection					X			X			
PD biomarkers 					X			X			
Pregnancy test 	X	X	X	X	X	X		X			
Evaluate transfusion frequency 	X	X	X	X	X	X		X	X		
Administer ACE-536 	X	X	X	X	X	X					
Monitoring for AEs of special interest  (Refer to Section 14.1 for details)	After signing ICF and until at least 3 years post last dose of IP or until death, loss to follow up, withdrawal of consent for further data collection.										
Survival follow-up 										X	X
Concomitant medications and AEs	Collected Continuously										

 **Screening procedures:** Other than informed consent, procedures listed as part of the 28-day screening period are only applicable to patients with treatment interruption. Patients with treatment interruption will need to qualify per the additional inclusion criteria listed in Section 9.2.1. For patients without treatment interruption, C1D1 may coincide with EOT visit of the base study A536-03. Procedures that are required to confirm eligibility for patients without treatment interruption can be performed at the base study A536-03 EOT visit and used to confirm eligibility prior to dosing on C1D1 of study A536-05.

 **Study procedures** must be done prior to administration of study drug. For patients without treatment interruption, C1D1 procedures shaded grey may be conducted as part of the EOT visit for study A536-03 and may not need to be repeated for study A536-05. All screening and Cycle 1 Day 1 procedure results required to confirm eligibility must be obtained and reviewed prior to study drug administration in A536-05.

**Visit schedule:** Each dosing visit (cycles 1-87) will be 21 days ( $\pm$ 5 days) from the previous dosing visit, unless a dose delay is required. If a dose delay is required per the dose modification rules (Section 10.8), the patient will not be dosed. The patient will return every 1-3 weeks for assessment of hematology results and AEs until the patient is eligible to receive the next dose of ACE-536 and start the next cycle. The patient should resume the study at the planned dosing cycle (e.g. if the patient missed a dose at C4D1, then they would resume dosing at C4D1 and not skip to C5D1).

**Dosing:** The patient dose must be calculated based on the patient's weight on the day of dosing. Dose modification rules and titration rules must be reviewed and implemented prior to dosing as required per protocol (see Section 10.8 and Section 10.9). A dose titration cannot occur until C3D1.

 **Medical History:** Medical history for patients with treatment interruption will include medical events occurring after EOS visit in study A536-03 and prior to C1D1 for study A536-05. Medical history for patients without treatment interruption will be taken from study A536-03.

 **Quality of life questionnaires** are only required on C1D1, C5D1, C9D1, C13D1, C17D1, C25D1, C33D1, C41D1, C49D1, C57D1, C65D1, C73D1, C81D1, EOT, and EOS.

 **Vital signs** will include weight, heart rate, and systolic and diastolic blood pressure.

 **ECG:** May be collected within 28 days prior to C1D1.

 **Bone marrow aspirate:** Patients with treatment interruption must have a bone marrow aspirate including cytogenetics performed  $\leq$  3 months prior to C1D1 for evaluation of eligibility per inclusion criteria Section 9.2.1. A bone marrow aspirate will not be performed on C1D1 for patients without treatment interruption. A bone marrow aspirate must be performed within 21 days after C9D1, C17D1, C25D1, C41D1, C57D1, and C73D1 for all patients. At the EOT visit, a bone marrow aspirate is required for all patients, unless performed  $<$  3 months following a previous bone marrow aspirate and not clinically indicated. Refer to the Laboratory Manual for processing and shipping instructions.

 **Serum Iron Studies:** May include serum iron, TIBC, transferrin, soluble transferrin receptor, ferritin.

 **Hematology:** RBC, WBC with differential, hemoglobin, hematocrit, nucleated red blood cells (nRBC), reticulocyte count, platelet count, peripheral blasts, mean corpuscular volume (MCV), mean corpuscular hemoglobin (MCH), mean corpuscular hemoglobin concentration (MCHC), and red blood cell distribution width (RDW). On dosing days, hemoglobin values may be drawn and resulted (up to 1 day) prior to dosing (see Section 10.8, Individual Dose Modification Rules).

 **Serum Chemistry:** Sodium, potassium, AST, ALT, lactate dehydrogenase (LDH), total bilirubin, direct bilirubin, alkaline phosphatase, blood urea nitrogen (BUN)/urea, creatinine, gamma-glutamyl transpeptidase (GGT), calcium, phosphorus, glucose, amylase, lipase, total protein, albumin, and uric acid.

 **Urinalysis by dipstick analysis (local lab):** pH, specific gravity, protein, glucose, ketones, blood, leukocyte esterase, and nitrite, with microscopic examination if indicated. **Urine Chemistry (central lab):** urine chemistries include but are not limited to: microalbumin and creatinine.

 If the patient has a **positive ADA** result at their last assessment, the patient may be asked to return approximately every three months for additional testing, until a negative result is obtained or the result is considered stabilized.

 **PD Biomarkers:** May include hepcidin, GDF15, GDF8, GDF11, Activin A and others to be determined.

 **Pregnancy test:** (urine or serum) is required for female patients of child bearing potential only.

 **Transfusion Frequency:** Transfusion history will be collected from the EOS visit in the base study A536-03 through the C1D1 visit of A536-05 as available for patients with treatment interruption up to 24 weeks. TD patients will have a defined "pre-transfusion hemoglobin threshold" for requiring transfusion during the study which will be calculated based on transfusion history and will be used for determining when to transfuse during the study. The baseline pre-transfusion hemoglobin threshold will be the mean of all documented pre-transfusion hemoglobin values during the 12 weeks prior to C1D1 of base study A536-03 (for TD patients without treatment interruption) or study A536-05 (for TD patients with treatment interruption). During treatment, if the pre-transfusion hemoglobin level is increased by  $\geq$  1 g/dL compared to the baseline pre-transfusion hemoglobin threshold for that patient, transfusion should be delayed by a minimum of 7

days and/or the number of units transfused should be reduced by 1 or more RBC units. Patients should not be transfused if hemoglobin is  $\geq 9$  g/dL unless indicated for symptoms related to anemia or other reasons at the investigator's discretion.

 **Cycles 16 through 87:** Patients may complete up to 87 Cycles. The last dose of ACE-536 may not be administered after 87 cycles or 1825 calendar days from C1D1, whichever occurs first.

 **End of Treatment (EOT):** Should be performed 28 days ( $\pm 7$  days) after the last dose of ACE-536. Patients who discontinue treatment early should complete the EOT visit at the time of discontinuation, followed by PTFU, LTFU, and EOS visits.

 **Post-Treatment Follow-Up (PTFU):** Patients will complete the PTFU visit 2 months ( $\pm 7$  days) after the last dose of ACE-536

 **Long-Term Follow-Up (LTFU):** Patients will complete LTFU visits every 3 months ( $\pm 7$  days) after the last dose of ACE-536 for 3 years after the last dose of ACE-536.

 **End of Study (EOS):** Should be performed 3 years after the last dose of ACE-536.

 Long-Term Post-Treatment Follow-Up for overall survival (OS), progression to AML, other malignancies/pre-malignancies (please refer to Section 14.1 for details) may be conducted by record review (including public records if allowed by local regulations) and/or telephone contact with the patient, family, or the patient's treating physician. The investigator must make every effort to obtain information regarding the patient's survival status before determining the patient is lost to follow-up.
